9.6 Pregnancy

The Investigator must make every effort to try and ensure that a clinical trial patient or a partner of a clinical trial patient does not become pregnant during the trial or for six months afterwards. This should be done as part of the consent process by explaining clearly to the patient the potential dangers of becoming pregnant and also providing each patient with information about appropriate medically approved contraception. Two forms of medically approved contraception should be used, such as:

- oral contraceptives and condom; (oral, injected or implanted hormonal contraceptives should be used for four weeks before the patient joins the study)
- intra-uterine device (IUD) and condom;
- diaphragms with spermicidal gel and condom.

Contraceptives should be used throughout the trial and for six months after completing the trial.

It should be explained to the patient that if his partner is pregnant or breast-feeding when he enters the trial, the patient should use barrier method contraception (condom plus spermicidal gel) to prevent the unborn baby or the baby being exposed to vandetanib or selumetinib.

However, if a patient or a partner of a patient does become pregnant, the reporting procedures below must be followed.

Any pregnancy occurring in a patient or a patient's partner during treatment with an IMP or occurring within six months of last IMP administration must be reported to the PV Department within 24 hours of the site staff becoming aware of it using a Pregnancy Notification Form. It is the Investigator's responsibility to obtain consent for follow-up from the patient or patient's partner. The PV Department will follow-up all pregnancies for the pregnancy outcome via the Investigator, using a Pregnancy Outcome Form.

The Investigator must ensure that all patients are aware at the start of a clinical trial of the importance of reporting all pregnancies (in themselves and their partners) that occur whilst being treated with the IMP and occurring up to six months after the last IMP administration. It is the Investigator's responsibility to ensure the patient's partner is aware that consent is collected from them in order for CRUK CDD to collect follow up information for the

CONFIDENTIAL

pregnancy including the outcome of the pregnancy and the baby's health following birth, on a Pregnancy Outcome Form. In case the partner of a patient becomes pregnant, a consent form should be provided to the patient's partner in order to obtain consent for collecting privacy data in accordance with the data protection act. The Investigator should offer counselling to the patient and/or the partner, and discuss the risks of continuing with the pregnancy and the possible effects on the foetus. Monitoring of the patient and the baby should continue until the conclusion of the pregnancy, if the patient or patient's partner has consented to this.

10 ASSESSMENT OF EFFICACY

10.1 Measurement of disease

Disease must be measured according to the RECIST (version 1.1) criteria given in Appendix 3.

10.2 Timing and type of tumour assessments

A thorough clinical and radiological evaluation of malignancy, as judged appropriate by the Investigator, and in line with the protocol, must be performed before starting the investigational medicinal product (IMP). The same methods that detect evaluable lesions at baseline must be used to follow these lesions throughout the trial. To ensure compatibility, the radiological assessments used to assess response must be performed using identical techniques. Imaging based evaluation is preferred to evaluation by clinical examination when both methods have been used to assess the anti-tumour effect of a treatment.

All radiological assessments must be performed within four weeks before starting treatment. The interval between the last anti-cancer therapy and these measurements must be at least four weeks (28 days). All clinical measurements to assess response must be done within **one** week before the patient starting treatment.

All complete (CR) and partial responses (PR) must be confirmed by two consecutive observations not less than four weeks apart. All stable disease (SD) must be confirmed by two consecutive observations not less than six weeks apart.

Copies of the scans must be available for external independent review if requested by the Centre for Drug Development (CDD).

Baseline evaluations

These must include radiological measurements as indicated (chest computerised tomography (CT) scan, abdominal CT scan, magnetic resonance imaging (MRI), bone scan) and/or clinical measurements as appropriate. All areas of disease present must be documented (even if specific lesions are not going to be followed for response) and the measurements of all measurable lesions must be recorded clearly on the scan reports. Any non-measurable lesions must be stated as being present. For clinical measurements, documentation by colour photography including a ruler to estimate the size of the lesion is strongly recommended, as this aids external independent review of responses. (See Section 1.2.1 of RECIST (version 1.1) criteria)

Evaluations during and at 'off-study'

Tumour assessments must be repeated every six weeks or more frequently, when clinically indicated. All lesions measured at baseline must be measured at every subsequent disease assessment, and recorded clearly on the scan reports. All non-measurable lesions noted at baseline must be noted on the scan report as present or absent.

All patients, who are removed from the trial for reasons other than progressive disease, must be re-evaluated at the time of treatment discontinuation, unless a tumour assessment was performed within the previous four weeks.

It is the responsibility of the Principal Investigator to ensure that the radiologists are aware of the requirement to follow-up and measure every target lesion mentioned at baseline and comment on the non-target lesions in accordance with RECIST criteria.

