1.2 Clinical trial objectives and endpoints**Primary objectives and endpoints**

Primary objectives	Endpoints
Assessing the safety and toxicity profile of the combination of vandetanib and selumetinib.	Determining causality of each adverse event to vandetanib or selumetinib and grading severity according to NCI CTCAE Version 4.02
To propose a recommended dose and schedule for Phase II evaluation of the combination of vandetanib and selumetinib.	Determining the MTD of the combination of vandetanib and selumetinib as proposed by the protocol. OR the single agent recommended Phase II dose (RP2D) of vandetanib in combination with the single agent RP2D of selumetinib.

Secondary objectives and endpoints

Secondary objectives	Endpoint
Determine the plasma pharmacokinetic (PK) profiles of vandetanib and selumetinib and their metabolites	PK parameters during Cycle 1 including Cmax and AUC pre and post treatment with vandetanib alone and following the combination of vandetanib and selumetinib. Parameters to be measured include: 
• vandetanib• selumetinib and N-desmethyl metabolite. (other metabolites may be measured as determined during the study).
Expansion cohort To evaluate progression free survival (PFS) of patients with NSCLC after treatment with the combination of vandetanib and selumetinib.	Determine PFS at 12 weeks (measured from date of first dose of vandetanib) by RECIST (Response Evaluation Criteria In Solid Tumors) criteria.
Expansion cohort To evaluate the survival rate of patients with NSCLC after treatment with the combination of vandetanib and selumetinib.	Determine the one year survival rate.
Expansion cohort To assess the tumour metabolism in patients with NSCLC.	Measurement of tumour metabolism using CT FDG-PET imaging during Cycle 1 pre and post treatment with vandetanib alone and following the combination of vandetanib and selumetinib.

Tertiary objectives and endpoints

Tertiary objectives	Endpoint
[REDACTED]	[REDACTED]

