3.2.2 Expansion cohort

Once the RP2D of the combination has been determined, a further 30 NSCLC patients will be treated at this dose level.

All patients will continue to be assessed for safety and tolerability of the combination treatment. All patients will be imaged and will also be asked to consider additional consent to

CRUKD/11/001 Protocol version 13.0 FINAL 26Jan2018

EudraCT number: 2011-000627-33

© Cancer Research UK

an optional biopsy sampling schedule. It is expected that a minimum of 20 patients will complete the full imaging schedule and a minimum of 10 patients will consent to be biopsied. Patients who undergo the additional biopsies may also complete the full imaging schedule if further evaluable lesions are identified.

Imaging will be performed to measure tumour vascularisation and metabolism using FDG-PET [REDACTED] These functional imaging assessments will take place pre and post treatment with single agent vandetanib and following combination treatment with selumetinib. [REDACTED]
[REDACTED]
[REDACTED]

Progression free survival will be assessed at 12 weeks and one-year survival will also be recorded.

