7.1.2 Evaluations within four weeks (28 days)

The following must be performed/obtained **within the four weeks before** the patient receives the first dose.

- Written informed consent (as detailed in Section 7.1.1)
- Demographic details
- Medical history including prior diagnosis, prior treatment, concomitant diseases and concomitant treatment
- Radiological Disease Assessments every 2 cycles
 - To include thoracic CT in expansion cohort
 - Radiological measurements using the most appropriate imaging for each patient using computerised tomography (CT) scan or magnetic resonance imaging (MRI) –must be performed **within four weeks before** the patient receives the first dose
- Bone scan (optional as clinically indicated)
- Ophthalmological exam (including slit lamp, visual acuity, visual fields, colour vision, optical coherence tomography (OCT) and intraocular pressure)
 - Adverse events relating to visual function have been reported in all studies with selumetinib to include blurred vision (please see IB supplement for further details of visual function toxicity). Therefore eye exams have been built into the schedule of events to allow for continuous assessment throughout study treatment.

Note that all adverse events (AEs), including serious adverse events (SAEs), must be monitored and recorded in the eCRF from the time the patient consents to any protocol-specific procedure (see Section 9 for further details).

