7.2 Evaluations during the trial

This section describes the evaluations that must be undertaken during the trial.

The following assessments should be performed throughout the trial period.

Adverse events and concomitant treatments: At each visit, before each IMP administration, an assessment of any AE experienced since the previous visit must be made by the Investigator or Research Nurse and the start and stop dates of the AE together with

the relationship of the event to treatment with vandetanib or selumetinib must be recorded in the medical records. All AEs must be graded according to NCI-CTCAE Version 4.02. Any concomitant treatment must also be recorded in the medical records and eCRF. (See Section 9 for further details regarding AE reporting requirements.)

Radiological assessment of disease (to include thoracic CT in expansion cohort):

Following the baseline assessment (Section 7.1.2), radiological assessment must be performed every two cycles. If a patient comes off study for reasons other than progressive disease, this should also be repeated at the off study visit, 28 days after the last drug administration, unless such assessment has been performed within the previous four weeks.

7.2.1 Evaluations during Cycle 1

This section describes the evaluations to be undertaken during the first cycle of study treatment. The first cycle is defined as administration of single agent vandetanib (14 days to include the loading phase) and administration of vandetanib and selumetinib in combination for 28 days (therefore a total of 42 days). For cycle definitions please see Section 1.4.3.

Therefore in Section 7.2.1, evaluations will be described between Days 1 and 42.

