7.2.3 Evaluations for Cycle 3 onwards

Required for dose escalation and expansion cohorts

- **Cycle 3 Day 1:** Ophthalmological exam (as per 7.1.2) (within 7 days prior to Cycle 3 Day 1 is acceptable).

On the first day of each cycle (-3 days allowable), prior to dosing

- Physical examination: symptom-directed physical examination.
- WHO performance status, temperature, pulse rate and BP (sitting) and weight.
- Haematology tests: detailed in Section 7.1.4;
- Biochemistry tests: detailed in Section 7.1.4;
- Ophthalmological exam (as per 7.1.2) (for patients experiencing visual disturbances), as clinically indicated. ECG

7.2.4 Evaluations (radiological) at Week 10

- The first radiological assessment of disease (to include thoracic CT in expansion cohort) should be performed following completion of Cycle 2 of combination treatment i.e. Week 10. Radiological assessment to be performed every two cycles thereafter.

Expansion cohort (Cycle 1) ONLY

- [REDACTED]

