7.6 Schedule of events (2)

Cycle 2 of combination (vandetanib and selumetinib) onwards

Observation/Investigation	Standard Evaluations for each cycle 1 cycle = 28 days (vandetanib and selumetinib treatment)				10 weeks* (Post end Cycle 2)	12 weeks	Off study and Follow-up	
	Day 1	Day 8	Day 15	Day 22			Off study: 28 days after last dose of IMP	Follow-up: monthly(s)
Adverse event evaluation	Continually review						X	Until resolution
Concomitant treatments	Continually review						X	
Radiological (CT, MRI, X-ray) disease assessment (to include thoracic CT) (m)	To be performed every two cycles				X		X (unless performed within previous 4 wks)	
Ophthalmological exam (n)	C2D1, C3D1 and as clinically indicated throughout study treatment for patients experiencing visual disturbances							
Clinical disease assessment (if applicable)	As clinically indicated						As clinically indicated	
Physical examination	On the first day of each cycle: symptom-directed physical examination						Symptom-directed physical examination	
Temperature, blood pressure and pulse	On the first day of each cycle						X	
Weight	On the first day of each cycle						X	
WHO performance status	On the first day of each cycle						X	
Laboratory tests: haematology and biochemistry (o)	X	X	X	X			X	To resolution of drug-related lab AEs
GFR assessment	As clinically indicated (calculated C&G/Wright and if applicable Isotope clearance measurement)							
Urinalysis	As clinically indicated						X	
Electrocardiogram (ECG) (p)	Prior to Day 1 of every cycle						X	
ECHO/MUGA (q)	C2D1 and then every 12 weeks (or more often as clinically indicated)							
Vandetanib administration (t)	Continuous daily dosing – Doses and schedule of each IMP to be confirmed by the Sponsor							
Selumetinib administration (t)	Continuous daily dosing – Doses and schedule of each IMP to be confirmed by the Sponsor							
Expansion cohort only (NSCLC patients)								

(m) Bone scan to be performed as clinically indicated.

(n) To include slit lamp assessment, visual acuity, visual fields, colour vision, optical coherence tomography and intraocular pressure. Examinations must be performed prior to Cycle 2 Day 1 and Cycle 3 Day 1 (within 7 days prior to C2D1 and C3D1 is acceptable). Additional eye examinations can then be performed as clinically indicated.

(o) Haematology and biochemistry to be assessed weekly during Cycle 1 and 2 and then prior to Day 1(-3 days time window) of subsequent cycles.

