In the event of a Grade 4 neutropenia or Grade 4 thrombocytopenia a full blood count must be performed at least on Day 5 after the onset of the event to determine if a dose limiting toxicity has occurred. Continue close monitoring until resolution to Grade 3 or less.

(p) More frequent ECGs required in patients with symptoms symptomatic of cardiac impairment.

CONFIDENTIAL

- (q) MUGA/ECHO to be performed prior to Cycle 2 Day 1 (within 7 days prior to C2D1 is acceptable) then ECHOs and MUGAS to be performed every 12 weeks or more often as clinically indicated
[REDACTED]
- (s) Monthly follow-up required ONLY for those AEs and SAEs considered drug-related (highly probable, probable or possible) that are present at time that patient comes off the trial. Monthly follow-up to continue until resolution, to baseline, stabilisation or patient starts another anti-cancer treatment
- (t) Alternate doses may be investigated – the Sponsor will confirm doses and schedule of each study drug for each new cohort. Please see section 3.2

***To note: First radiological assessment to be performed at the end of Cycle 2. Thereafter radiological assessment to be performed every two cycles.**

CONFIDENTIAL

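### Sections 10.2 and 7 set incompatible scan calendars, the visible Section 7 calendar has no routine scan at the 12-week PFS landmark, and the response-confirmation and stable-disease rules also conflict

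*Protocol*

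**What the plan says.** **Scan calendar.** Section 10.2: "Tumour assessments must be repeated every six weeks or more frequently, when clinically indicated". No starting date is given.

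Section 7 says otherwise in five places:
- Section 7.1.2: "Radiological Disease Assessments every 2 cycles".
- Section 7.2, after the baseline assessment: "radiological assessment must be performed every two cycles".
- Section 7.2.4 places the first scan "following completion of Cycle 2 of combination treatment i.e. Week 10. Radiological assessment to be performed every two cycles thereafter".
- Section 7.6, radiology row: "To be performed every two cycles". The row is marked in the 10-week and off-study columns; nothing is visible under 12 weeks.
- Section 7.6, note below the table: "First radiological assessment to be performed at the end of Cycle 2. Thereafter radiological assessment to be performed every two cycles".

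**Endpoint.** Section 3.2.2: "Progression free survival will be assessed at 12 weeks". Sections 1.2 and 3.1 count the 12 weeks from the first vandetanib dose and use RECIST. Section 13 attaches a test to this rate: 9% against 23%, 30 patients, 82% power, one-sided 10% level.

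**Response rules.** Sections 3.1.3, 10.2 and 10.3 all require complete and partial responses to be confirmed at least four weeks later. Appendix 16.3 (item 2.4.3) states that in this trial no confirmation is needed, yet its Table 3 is the table for trials that do require it. For stable disease (SD), Section 10.2 asks for two successive assessments at least six weeks apart. Section 10.3 asks for one, at least six weeks after the first dose of study drug. Section 3.1.3 asks for one, at least six weeks after the first combination dose.

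**The concern.** A first scan at ten weeks followed by eight-week intervals cannot satisfy a six-weekly requirement, so a site obeying one section deviates from the other. If sites resolve the conflict differently, patients within one 30-patient cohort are not assessed on the same basis.

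The landmark makes this matter. Progression by RECIST is established at an assessment. If scans fall at weeks 10 and 18, status at week 12 must be inferred, and the rate moves with the inference. The endpoint is secondary, and Section 2.3.1 disclaims power for firm efficacy conclusions, but it carries the protocol's only power statement.

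The confirmation and SD conflicts do not touch PFS. They change the best-response category, which Section 13.5 sends to data listings.

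**Working it through.** **1. Reproduce week 10.** Section 1.4.3 gives Cycle 1 as 42 days and later cycles as 28 days with no gap. 42 + 28 = 70 days = week 10, as stated. The next scan is 2 × 28 = 56 days later, at week 18.

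**2. Section 10.2 calendar under each possible origin.**

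| Origin | Scan weeks, counted from first dose |
|---|---|
| First vandetanib dose | 6, 12, 18 |
| Baseline scan, 0 to 4 weeks before dosing | 2–6, 8–12, 14–18 |
| Start of combination (Day 15) | 8, 14, 20 |
| Section 7, for comparison | 10, 18 |

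Only the first-dose origin reliably gives a scan at week 12. The baseline origin does so only when the baseline scan coincides with the first dose.

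**3. Direction of the error, without a model.** The Section 7 scans fall 2 weeks before and 6 weeks after the landmark. A PFS curve cannot rise. Status carried from week 10 therefore cannot understate the week-12 rate, and status that requires the week-18 scan cannot overstate it.

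**4. Size, as an illustration.** Assume constant hazard and progression found only at scheduled scans: S(t) = S(12)^(t/12).

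- Week 10: 0.09^(10/12) = 0.134; 0.23^(10/12) = 0.294.
- Week 18: 0.09^(18/12) = 0.027; 0.23^(18/12) = 0.110.

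Section 13 states no cut-off, so two are shown. The normal approximation at one-sided 10% gives a critical count of 4.71, that is 5 of 30, with power 82.9%, close to the stated 82%. The smallest count with an exact p-value at or below 10% is 6 of 30. Exact binomial chance of success, n = 30:

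| Cut-off | True 12-week rate | Read at week 10 | Read at week 12 | Read at week 18 |
|---|---|---|---|---|
| 5/30 | 9% | 37.8% | 12.8% | 0.1% |
| 5/30 | 23% | 96.5% | 85.2% | 23.1% |
| 6/30 | 9% | 20.8% | 4.8% | 0.01% |
| 6/30 | 23% | 91.3% | 71.9% | 10.6% |

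Limits: constant hazard through 9% at week 12 implies a median of 3.5 weeks, against the 11 weeks quoted for vandetanib in Section 2.2.1.6. A Weibull curve through both points would need a shape of about 14. The scan schedule behind the 9% is unknown. The gaps shrink to nothing as more progressions are dated when they occur.

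**5. Stable disease on the Section 7 calendar.** The week-10 scan is at about Day 70.

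- Section 10.3: Day 1 + 42 = Day 43, passed.
- Section 3.1.3: Day 15 + 42 = Day 57, passed.
- Section 10.2: a second routine assessment is needed, and the earliest is week 18.

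A patient stable at week 10 and progressing at week 18 has SD under two sections and not under the third.

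**6. Confirmation.** The three body sections agree with one another. Item 2.4.3 of Appendix 16.3 stands alone, and Section 10.1 makes that appendix the binding method of measurement.

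**The case against.** **Redaction.** The schedule in Section 7.6 has a 12-week column, and the expansion-cohort rows beneath it are redacted, as is an expansion-cohort item in Section 7.2.4. A week-12 scan may be there. This stands as a limit: the claim covers the visible calendar only. A hidden entry would still leave Section 10.2 at odds with Section 7, whose unredacted note gives only week 10 and every two cycles thereafter.

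**Left to the SAP.** Assessment windows and the handling of progression between scans commonly belong there, and no text requires a week-18 scan before a patient counts as progression-free at week 12. Both points are fair, and the week-18 reading is the extreme case. But a SAP cannot tell sites when to scan or supply a scan that was not taken. A window wide enough to reach week 10 would in effect make week 10 the endpoint.

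**Unrealistic figures.** The illustration rests on an assumed curve and an assumed cut-off. Scans on clinical indication and at discontinuation would date some progressions between routine visits. If the 9% came from similarly spaced scans, part of the bias would cancel. This stands, and the conclusion does not depend on the figures.

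**One stray sentence.** Section 7 is consistent with itself, and nothing shows that sites have diverged. True, but Section 10.2 is worded as mandatory; its reference to clinical indication most naturally qualifies only scanning more often.

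**Baseline as the first SD observation.** If allowed, week 10 would satisfy all three rules. It does not hold: SD is defined by comparison with a reference sum, so baseline is not itself an SD assessment.

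**Conclusion.** The concern holds. The scan calendars, the confirmation rules and the SD rules each contradict one another in the protocol text, and none of this rests on a model. The absence of a routine week-12 scan holds for the visible Section 7 calendar only.

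The effect on the 12-week rate is certain in direction but not in size. The illustrative shifts, about 4 to 6 percentage points up (13.4 − 9 = 4.4; 29.4 − 23 = 6.4) or 6 to 12 down (9 − 2.7 = 6.3; 23 − 11.0 = 12.0), depend on constant hazard and on detection at scheduled scans alone. Because the endpoint is secondary and best response is only listed, this should be corrected but does not undermine the trial's primary objectives.

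**What to change.** 1. Reconcile Sections 7.1.2, 7.2, 7.2.4, 7.6 and 10.2 to a single scan calendar counted explicitly from the first vandetanib dose (Cycle 1 Day 1), with a scheduled scan at week 12.
2. If the Section 7 calendar is kept instead, define the endpoint at the week-10 scan and justify the 9% and 23% on that basis.
3. In Appendix 16.3, item 2.4.3, state that confirmation is required and refer to Table 3, matching Sections 3.1.3, 10.2 and 10.3.
4. Keep one SD rule with one time origin in Sections 3.1.3, 10.2 and 10.3.

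The cost is a protocol amendment. A six-weekly calendar from first dose means three scans in the first 18 weeks (weeks 6, 12 and 18) instead of two (weeks 10 and 18), which is no more than Section 10.2 already demands. Keeping the Section 7 calendar adds no scans but needs a source for week-10 rates, which the protocol does not give.
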